6.0 Correlative Studies

6.1 CTC enumeration by CellSearch (encouraged, but not required)

CTC counts by CellSearch (Veridex) methodology will be performed prior to study drug initiation (within 1 month), after study drug completion C2, and at progression. Samples should be analyzed by a CLIA certified lab and billed to subject's insurance. CTC counts are optional for institutions not able to perform this procedure due to insurance reimbursement or may arrange for central CTC enumeration (in this case, subjects will not be billed, but funding will be taken out of per-subject reimbursement for that site).

6.2 Blood for research analysis:

PBMCs and plasma for research will be collected on C1D1 (or within 4 weeks prior to treatment). Plasma will also be collected at the following time points: C1D8, and at progression or end of study. This will be collected for research purposes only and will not be billed to the subject. Blood samples should be collected, processed and shipped to the central laboratory per specifications in the Lab Manual.

6.3 Serum tumor markers

Serum for central analysis of chromogranin A and neuron specific enolase (and CEA at some time points) will be collected on D1 of every cycle and at progression/end of study. Blood samples should be collected, processed and shipped to the central laboratory per specifications in the Lab Manual.

6.4 Archival Tissue. Tissue blocks or 10 unstained slides (10 microns each) and 5 unstained slides (40 microns each) with corresponding H&E slide will be sent at time of enrollment.

6.5 Metastatic Biopsy tissue. Will be performed per institutional protocol, but should include at least 1 core biopsy; fresh tissue should be processed and shipped to the central laboratory per specifications in the Lab Manual.

7.0 Radiographic evaluation

The following radiographic evaluations must be performed according to the schedule outlined below:

- Bone scan, CT/MRI abdomen/pelvis, and CT of chest at baseline
- Bone scan, CT/MRI of abdomen/pelvis, and CT of chest will be repeated after every 3rd cycle until the subject is off-study
- In addition, scans will be performed for subjects with clinical signs or symptoms of progression at the investigators discretion
- Every effort should be made to use the same imaging technique for follow up evaluation as was utilized at baseline
- Should RECIST criteria for PR or CR be met at any imaging time point, investigators are urged to consider a repeat scan at least 4 weeks following the scan demonstrating response. In this instance, or if imaging is performed for clinical purposes earlier than scheduled per protocol, it is permissible to “reset” future imaging time points to every 3rd cycle following the last scan.

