5.2.11 At progression

- Targeted Physical Examination with vital signs and weight
- Adverse event evaluation
- ECOG Performance Status

- PSA
- CBC with differential and platelet count
- Electrolytes, BUN, Creatinine
- Total protein, albumin, total bilirubin, AST, ALT, Alkaline phosphatase, Lactate dehydrogenase (LDH), uric acid
- Serum level of chromogranin A, neuron specific enolase, carcinoembryonic acid- central labs (can be performed at progression or end of study)
- CTC count (CellSearch)- optional
- Blood for research
- Optional metastatic tumor biopsy for research
- CT or MRI (abdomen-pelvis) plus CT of chest within 2 weeks of progression visit
- Bone scan

5.2.12 End of study (must occur > 30 days after last dose of study drug; research lab procedures performed as part of progression visit do not need to be repeated).

- Targeted Physical Examination with vital signs and weight
- Adverse event evaluation
- ECOG Performance Status
- PSA
- CBC with differential and platelet count
- Electrolytes, BUN, Creatinine
- Total protein, albumin, total bilirubin, AST, ALT, Alkaline phosphatase, Lactate dehydrogenase (LDH), uric acid
- Serum level of chromogranin A, neuron specific enolase, carcinoembryonic acid- central labs (can be performed at progression or end of study)
- CTC count (CellSearch) - optional
- Blood for research (can be performed at progression or end of study)

Standard lab evaluations (including CBC, chemistry exams) may be performed at approved CLIA certified local laboratories with the investigator's pre-approval.

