8.10 Termination of Treatment and/or Study Participation

Patients will be informed that they have the right to withdraw from the study at any time for any reason, without prejudice to their medical care. The investigator will withdraw patients from the study for any of the following reasons:

- Occurrence of an unacceptable adverse event
- A treatment cycle delay of >3 weeks because of toxicity
- Patient request
- General or specific changes in the patient's condition unacceptable for further treatment in the judgment of the investigator
- Progressive disease at any time

At the time of withdrawal, all study procedures outlined for the End of Study visit should be completed. The primary reason for a patient's withdrawal from the study is to be recorded in the source documents.

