- Withdrawal of patient consent
- Noncompliance with protocol-specified procedures which in the opinion of the investigator will expose subjects to undue risk or will significantly effect interpretation of study results

12. Statistical Considerations.

12.1. Sample Size Justification:

The primary endpoint is the proportion of patients who are free from radiographic progression at 6 months following treatment with MLN8237. Based on the phase II trial by Meulenbeld et al (BJUI 2012), the proposed null hypothesis (H_0) is that $\leq 15\%$ of patients will be radiographic progression-free at 6 months and the alternative hypothesis (H_a) is that $\geq 30\%$ of patients will be radiographic progression-free at 6 months.

Sample size recommendations for the phase II design are determined according to Ahern's exact single-stage phase II design (A'Hern RP, 2001). We project a 6-month radiographic progression-free proportion of 15%, below which the response will be unacceptable, and a 6-month radiographic progression-free proportion of 30%, above which the regimen will be considered worthy of further exploration. The null hypothesis that the 6-month radiographic progression-free proportion is less than or equal to 15% will be tested against the alternative hypothesis that the 6-month radiographic progression-free proportion is greater than or equal to 30%.

The sample size computations were performed assuming a 5% level of significance and 80% power. A total of 48 patients will be required to enroll in the study. The treatment will be declared effective and worthy of further testing if 12 or more patients are free from radiographic progression at 6 months among the 48 patients entered into the study. This exact single-stage design yields a ≥ 0.80 probability of a positive result if the true percentage of patients who are free from radiographic progression at 6 months is $\geq 30\%$. It yields a ≥ 0.95 probability of a negative result if the true percentage of patients who are free from radiographic progression at 6 months is $\leq 15\%$. Assuming 10-20% of patients will be unevaluable/ineligible, we anticipate that a total 60 patients will be enrolled in the study.

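### Scheduled scans end at off-study, so a patient who leaves early without progression has no 6-month status, and the denominator for such patients is unreconciled

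*Protocol*

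**What the plan says.** **Endpoint and rule.** Section 12.1 states: "The primary endpoint is the proportion of patients who are free from radiographic progression at 6 months following treatment with MLN8237". The treatment is declared worthy of further testing if "12 or more patients are free from radiographic progression at 6 months among the 48 patients entered into the study".

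**Scans.** Section 7.0 requires bone scan, CT/MRI of abdomen and pelvis, and CT of chest at baseline. These "will be repeated after every 3rd cycle until the subject is off-study". Additional scans for signs or symptoms of progression are at the investigator's discretion.

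**Leaving the study.** Section 8.10: "The investigator will withdraw patients from the study for any of the following reasons". The reasons include an unacceptable adverse event, a toxicity delay of more than 3 weeks, an unacceptable change in condition, patient request and progression. Section 8.2.1 also removes from the study patients who need more dose reductions than the table allows.

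**Afterwards.** Section 5.2.13 describes survival follow-up only, with no office visit needed. Section 8.10 asks for the End of Study procedures at withdrawal. The study calendar marks CT/MRI and bone scan at that visit, but the Section 5.2.12 list contains no imaging. Section 5.2.12 says the visit "must occur > 30 days after last dose of study drug".

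**Who is counted.** Section 4.2 includes all registered subjects in the final intent-to-treat analysis and lets those who do not complete one cycle be replaced. Section 12.1 assumes that 10-20% "of patients will be unevaluable/ineligible, we anticipate that a total 60 patients will be enrolled in the study".

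**The concern.** The endpoint is a status at a fixed time, so each patient needs either a documented progression before month 6 or a progression-free scan around it. The schedule ties scans to being on study. Some of the reasons for leaving (toxicity, clinical decline) are plausibly related to prognosis. If patients without a status are set aside as unevaluable, the observed proportion and the type I error can rise. Treating them as free because no progression was recorded would also raise the estimate. If they are kept as failures without further scans, power falls. The protocol does not reconcile which of these applies, and no later analysis plan can recover scans that were never taken.

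**Working it through.** **1. The plan's own design.** Inputs from Section 12.1: null rate 0.15, alternative 0.30, n = 48, success at 12 or more. On the error rates it says: "The sample size computations were performed assuming a 5% level of significance and 80% power". With X binomial:

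- P(X ≥ 12 | 48, 0.15) = 0.0478
- P(X ≥ 12 | 48, 0.30) = 0.8186

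A search for the smallest n with exact type I error at most 0.05 and power at least 0.80 returns 48 with cut-off 12. Enrolment: 48/0.90 = 53.3, so 54; 48/0.80 = 60. The stated design reproduces.

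**2. Where the 6-month scan falls.** Scans follow every third 21-day cycle: days 63, 126 and 189. Six months is about 182.6 days (6 × 30.44), so the nominal assessment is the day-189 scan. Cycle delays (Section 8.2.1) and the permitted reset of imaging dates (Section 7.0) move it.

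**3. A patient who stops at month 2 without progression.** Section 8.10 takes him off study, Section 7.0 then ends scheduled scans, and Section 5.2.13 follows survival. The End of Study scan, if done, falls more than 30 days after the last dose, so possibly around month 3. Progression on it is an observed failure. A clean result does not establish status at month 6. Only if the drug stopped near month 6 could that scan serve. A withdrawal at the patient's request loses the status in the same way; a toxicity stop after month 6 loses nothing.

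**4. If such patients are excluded.** The share lost, m, is not given in the protocol. I take m = 10-20%, borrowed from the Section 12.1 allowance, as an assumption. Let s be the success rate the lost patients would have had. With a true all-patient rate of 0.15, the rate among those analysed is (0.15 − m·s)/(1 − m), and the type I error is P(X ≥ 12 | 48, that rate).

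| s | m = 10%: rate, type I error | m = 20%: rate, type I error |
|---|---|---|
| 15% (loss unrelated to outcome) | 0.150, 4.8% | 0.150, 4.8% |
| 7.5% | (0.15 − 0.0075)/0.90 = 0.158, 6.7% | (0.15 − 0.015)/0.80 = 0.169, 9.9% |
| 0% (worst case) | 0.15/0.90 = 0.167, 9.2% | 0.15/0.80 = 0.188, 17.6% |

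**5. If they are counted as failures but still not scanned.** With loss independent of outcome, the success rate under the alternative becomes 0.30(1 − m). Power at 12 of 48 is P(X ≥ 12 | 48, 0.27) = 67.5% for m = 10% and P(X ≥ 12 | 48, 0.24) = 49.1% for m = 20%.

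**6. If all 60 are analysed, as Section 4.2 suggests.**

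| Cut-off of 60 | Type I error at 15% | Power at 30% |
|---|---|---|
| 12 | 18.1% | 97.1% |
| 14 | 5.8% | 90.0% |
| 15 | 2.9% | 83.8% |

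The cut-off of 12 does not carry over to 60 patients.

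**The case against.** Four points deserve weight.

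- **The intent-to-treat sentence.** Section 4.2 argues against exclusion, and nothing in Section 12.1 says that toxicity withdrawals are the unevaluable patients; the allowance also covers ineligible ones. This stands: exclusion is possible, not prescribed. But Section 4.2 does not fit a rule written for 48.
- **The analysis plan.** How a missing status is classified is commonly settled there, and that plan is not shown. That stands for the classification alone. The imaging schedule and withdrawal rules are protocol content.
- **The End of Study scan.** It will catch some early failures. It does not give month-6 status to an early stopper whose scan is clean.
- **Treatment versus study.** For the same delay of more than 3 weeks, Section 8.2.1 discontinues the drug while Section 8.10 withdraws the patient from the study; the heading of 8.10 covers either. Off-study is not defined. The text is inconsistent rather than uniform, which is itself a reason to settle it.

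A reader might infer that the endpoint is lost in exactly the toxicity stoppers, or that the protocol sets them aside and so inflates the error to 17.6%. The documents support neither. Other withdrawals lose the status too, late toxicity stoppers keep it, and 17.6% needs a full 20% excluded with no success among them.

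**Conclusion.** The gap in imaging is real and follows from the text: a patient who goes off study well before month 6 without progression has no scheduled scan that could establish the primary endpoint. The calendar and Section 5.2.12 disagree on the one scan that would partly help. The denominator is unreconciled between Sections 4.2 and 12.1, so exclusion is open. The size depends on an assumed 10-20% loss: from no effect on type I error (4.8%) when loss is unrelated to outcome, through 6.7-9.9%, to a worst case of 9.2-17.6%. The 48-patient design itself is correctly computed and needs no change if status is observed in all 48. This should be corrected, at modest cost.

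**What to change.** (a) In Section 7.0, for patients who stop the drug without radiographic progression and still consent, continue the existing scan interval (3 × 21 = 63 days, about 9 weeks) until radiographic progression, death or the 6-month assessment. Record any new anticancer therapy, since it complicates the reading of later scans.

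(b) Reconcile Section 5.2.12 with the calendar on End of Study imaging, and its timing with the instruction in Section 8.10 to complete the visit at withdrawal.

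(c) Reconcile Sections 4.2 and 12.1 by stating one denominator. Keep patients without a 6-month assessment in it and count them as not progression-free. Define a window around the nominal day-189 scan so that delayed or reset scans are not misclassified. Set the cut-off for that denominator, for example 15 of 60 (type I error 2.9%, power 83.8%).

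(d) Reconcile the passages on leaving treatment and leaving the study. No treatment-stopping rule is proposed here.

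**Cost.** One or two further scans per early stopper, on the existing interval. Item (c) is more than wording: it needs a new cut-off, and any status still missing lowers the estimate and power. Item (a) should therefore accompany it.

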8.0 Treatment Plan

8.1. Administration of MLN8237. Treatment will be administered only to eligible patients under the supervision of the investigator or identified co-investigator(s). Treatment will be administered on an outpatient basis. MLN8237 will be given PO in a dosage of 50 mg BID for 7 Days (Days 1-7) of each 21-day treatment cycle. The study drug will be administered on an empty stomach with the patient remaining NPO (nothing by mouth), except for water and prescribed medications, for 2 hours before and 1 hour after each dose. Patients will be instructed to take each oral dose of MLN8237 with 8 ounces (1 cup, 240 mL) of water. Appropriate dose modifications/delays for MLN8237 in section 5.2.

MLN8237 drug product is supplied as the ECT dosage form in 10 mg strength, with dose strength expressed as the milligrams of active drug (free acid). The key formulation excipients of the MLN8237 tablet formulation that aid in the in vivo absorption of the drug are the buffer (sodium bicarbonate), the surfactant (sodium lauryl sulfate), and the enteric coating. MLN8237 ECT are packaged in a 60-cc high-density polyethylene (HDPE) bottle with a rayon coil, induction seal, desiccant packs, and a

polypropylene child-resistant cap. MLN8237 is an anticancer drug, and as with other potentially toxic compounds, caution should be exercised when handling MLN8237.

All tablets are to be ingested whole; patients who have difficulty swallowing tablets will be excluded from the study. Antiemetic agents may be administered at the discretion of the investigator. Although not prohibited, the use of benzodiazepines for the prophylaxis or treatment of nausea or vomiting is discouraged because of the potential benzodiazepine-like effects of MLN8237.

Study drug will be administered only to eligible patients under the supervision of the investigator or identified subinvestigator(s)

8.2. Dose Modification and Delay

Toxicity will be evaluated according to the National Cancer Institute Common Terminology Criteria for Adverse Events (NCI CTCAE), Version 4.03. These criteria are available online at
http://ctep.cancer.gov/protocolDevelopment/electronic_applications/ctc.htm

8.2.1 Criteria for Retreatment and Dose Delay

Treatment with MLN8237 will be repeated every 21 days. In order for a new cycle of therapy to begin, the patient's ANC must be $\geq 1,500/\text{mm}^3$ and the platelet count must be $\geq 75,000/\text{mm}^3$. In addition, all other non-hematologic toxicity considered by the investigator to be related to therapy with MLN8237 must have resolved to \leq Grade 2 or to the patient's baseline values before a new cycle of therapy may begin.

If the patient fails to meet the above-cited criteria for retreatment, then initiation of the next cycle of therapy should be delayed for up to 1 week. At the end of that week, the patient should be re-evaluated to determine whether the criteria for retreatment have been met. Should treatment need to be delayed for more than 1 week (ie, a rest period of more than 21 days) because of incomplete recovery from treatment-related toxicity, the dose of MLN8237 will be reduced 1 level (Table 0-1) to 40 mg BID when therapy resumes. A second dose reduction to 30 mg BID may occur should treatment need to be delayed for more than 1 week because of incomplete recovery from treatment-related toxicity on the reduced dosage of 40 mg BID. Patients who require further dose reductions will be removed from the study. Should treatment need to be delayed for more than 3 weeks at any dose, therapy with MLN8237 will be discontinued.

Table 0-1 Table of Dose Adjustments

Dose Level	Dose	Schedule	Cycle Length
1	50 mg	PO BID	
-1	40 mg	PO BID	
-2	30 mg	PO BID	
-3		Discontinue	

Level 1 is the starting dose.

8.2.3. Dose Modifications for Hematological Toxicity

If a patient experiences any of the following hematological toxicities, dosing will be discontinued for the remainder of that cycle and the dose will be decreased 1 level for all subsequent cycles of treatment.

- Grade 3 neutropenia with fever or infection, or both, where fever is defined as an oral temperature greater than 38.5°C

- Grade 4 neutropenia (ANC < 500 cells/mm³) lasting more than 7 consecutive days. Patients experiencing Gr 4 neutropenia at any time should undergo repeat CBC within 5 days
- Grade 3 thrombocytopenia with clinically significant bleeding
- Grade 4 thrombocytopenia (platelet count < 25,000/µL) lasting more than 7 consecutive days.
- Patients experiencing Gr 4 thrombocytopenia at any time should undergo repeat CBC within 5 days.
- Platelet count less than 10,000/µL at any time

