8.2.4. Dose Modifications for Nonhematological Toxicities

If a patient experiences any of the following toxicities during the dosing period (i.e. D1-7 of the cycle), dosing will be discontinued for the remainder of that cycle and the dose will be decreased 1 level for all subsequent cycles of treatment, and treatment may resume after drug-related toxicities have resolved to \leq Grade 1 or to baseline.

- Any Grade 3 nonhematological toxicity that is considered by the investigator to be related to study drug other than:
 - Grade 3 arthralgias/myalgias
 - Grade 3 or greater nausea or emesis, or both, that occurs in the absence of optimal antiemetic therapy (5-hydroxytryptamine 3 [5-HT3] serotonin receptor antagonist)
 - Grade 3 or greater diarrhea that occurs in the absence of optimal supportive therapy with loperamide
 - Grade 3 fatigue that lasts less than 1 week
- Grade 2 nonhematological toxicities that are considered by the investigator to be related to study drug and in the opinion of the investigator require dose reduction.

In general, study drug treatment should be discontinued if a patient experiences any Grade 4 non-hematologic toxicity. If, in the opinion of the investigator and study sponsor it is in the patient's interest to continue therapy with MLN8237, then after recovery from the toxicity or toxicities in question to \leq Grade 1 or to baseline values, the dose of MLN8237 should be reduced by at least 1 dose level with subsequent cycles of therapy. When a dose reduction of MLN8237 is required, no re-escalation of dose will be permitted. If a patient requires more than 2 dose reductions, therapy with MLN8237 will be discontinued. Any additional dose delays or dose modifications should be discussed with the Study Chair.

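### Section 8.2.3 forces a dose reduction for febrile Grade 3 neutropenia and bleeding Grade 3 thrombocytopenia, but as worded not for the same complications at Grade 4 lasting 7 days or less

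*Protocol*

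**What the plan says.** Protocol Section 8.2.3 (Dose Modifications for Hematological Toxicity) lists the events that end dosing for the current cycle and lower every later cycle by one level:

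- "Grade 3 neutropenia with fever or infection, or both", with no duration condition;
- Grade 4 neutropenia (ANC below 500), qualified as "lasting more than 7 consecutive days. Patients experiencing Gr 4 neutropenia at any time" and followed only by a repeat blood count within 5 days;
- "Grade 3 thrombocytopenia with clinically significant bleeding", with no duration condition;
- Grade 4 thrombocytopenia (platelets below 25,000/µL), again only if it lasts more than 7 consecutive days;
- "Platelet count less than 10,000"/µL at any time.

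Two neighbouring sections bear on the same patients. Section 8.2.1 sets a retreatment gate ("In order for a new cycle of therapy to begin"): ANC at least 1,500/mm³, platelets at least 75,000/mm³, and related non-hematologic toxicity back to Grade 2 or lower or to baseline. It reduces the dose only under this condition: "Should treatment need to be delayed for more than 1 week (ie, a rest period of more than 21 days"). Section 8.2.4 has its own mandatory list for nonhematological toxicity, limited to events "during the dosing period (i.e. D1-7 of the cycle").

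**The concern.** A dose-modification rule should respond at least as strongly to the worse form of a complication as to the milder form. Here the Grade 3 bullets carry the complication (fever, infection or bleeding) and the Grade 4 bullets drop it, using duration or a very low platelet count instead. Read as written, a short Grade 4 episode with fever or bleeding falls between the two sets.

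The matter is one of patient safety. Section 1.3.6 lists febrile neutropenia, and thrombocytopenia with a risk of bleeding, among the known risks of the drug. The patients left out are those with the deeper cytopenia and the same complication. With up to 10 additional sites, leaving the reduction to judgment also means that sites may handle the same event differently.

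**Working it through.** **Inputs.** From Section 8.2.3: Grade 4 is ANC below 500 or platelets below 25,000/µL, the duration limit is more than 7 days, and the platelet floor is 10,000/µL. From Table 0-1: 50, 40 and 30 mg BID, then discontinuation. From Section 8.2.1: the retreatment counts and the 1-week delay limit. The upper limits of Grade 3 are not printed. ANC 800 and platelets 40,000 are taken as Grade 3 by assumption, and the result does not depend on those upper limits.

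**Step 1: apply the 8.2.3 triggers as worded, with the complication present.**

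| Event with fever/infection or bleeding | 3 days | 7 days | 8 days |
|---|---|---|---|
| ANC 800 (Grade 3) | reduce | reduce | reduce |
| ANC 300 (Grade 4) | no trigger | no trigger | reduce |
| Platelets 40,000 (Grade 3) | reduce | reduce | reduce |
| Platelets 20,000 (Grade 4) | no trigger | no trigger | reduce |
| Platelets 10,000 (Grade 4) | no trigger | no trigger | reduce |
| Platelets 9,000 (Grade 4) | reduce | reduce | reduce |

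For example, one day of fever with ANC just above 500 mandates a reduction. Five days of fever at ANC 300, with no fever or infection while ANC is 500 or above, does not.

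**Step 2: does the retreatment gate in 8.2.1 close the gap?** Dosing is D1–D7, so the planned rest is D8–D21 = 14 days and the next cycle starts on D22. A 1-week delay moves the start to D29, with a rest of 14 + 7 = 21 days. This reproduces the section's own 21-day figure; a reduction is required only beyond it. Take a Grade 4 episode on D8–D14 (7 days, so not more than 7):

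- recovery time is D15–D21 = 7 days for a D22 start, or D15–D28 = 14 days for a D29 start;
- ANC must rise more than 1,500/500 = 3-fold, or 1,500/300 = 5-fold from 300;
- platelets must rise between more than 75,000/25,000 = 3-fold and 75,000/10,000 = 7.5-fold.

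A patient who recovers in that time may restart at the same dose. Section 8.5 permits myeloid growth factors to treat neutropenia. The 8.2.1 gate, unlike eligibility criterion 4.3.6, does not ask for counts free of growth factor support.

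**Step 3: does 8.2.4 close it?** Its Grade 3 list covers D1–D7 only. Section 1.3.4 reports myelosuppression in the treatment-free period in 3 of 3 patients at 60 mg BID, which is above the study dose. The separate Grade 4 sentence in 8.2.4 has no day limit, but it needs a Grade 4 non-hematologic event.

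**Step 4: dose at stake per affected patient.** Dose per cycle = strength × 2 × 7.

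- From 50 mg BID: 50 × 2 × 7 = 700 mg against 40 × 2 × 7 = 560 mg; 140/700 = 20% lower.
- From 40 mg BID: 560 mg against 30 × 2 × 7 = 420 mg; 140/560 = 25% lower.
- From 30 mg BID: 420 mg against discontinuation.

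For an episode that starts after D7, only the reduction is at stake, because that cycle's dosing has already ended.

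**The case against.** The strongest reply is that the authors probably meant Grade 3 as a threshold, with the Grade 4 duration bullets covering uncomplicated cytopenia. Section 8.2.4 does write a floor explicitly when it wants one ("Grade 3 or greater diarrhea that occurs in the absence of optimal supportive therapy with loperamide"), which supports a literal reading of 8.2.3. But that phrase is an exception carved out of a rule about Grade 3 toxicity, so the drafting there is not strict either. This weakens the comparison between the two sections. It does not alter the bullets of 8.2.3, which treat Grade 3 and Grade 4 separately and omit the complication at Grade 4. Probable intent is a reason to correct the text.

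A second reply is that grading follows CTCAE v4.03, which is not reproduced. The Grade 4 limits that matter are printed in 8.2.3 itself, so the boundary does not need that source.

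A third is that several backstops remain, and this part stands as a limit on size:

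- If fever, infection or bleeding is present while counts pass through the Grade 3 range, the Grade 3 bullet applies. This depends on a blood count catching it, and from cycle 2 the Day 15 evaluation is discretionary (Section 5.2.9).
- A Grade 4 infection or bleed at any time generally leads to discontinuation under 8.2.4, or otherwise to a reduction of at least one level.
- Sections 3.0 and 8.10, and the referral to the Study Chair in 8.2.4, let investigators reduce or stop. Many would.

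The last group is discretionary and does not restore a mandatory rule. Same-dose retreatment is permitted, not required.

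**Conclusion.** The concern holds: Section 8.2.3 is wrong as written. It mandates a reduction for the milder event and not for the more severe one in two situations, each lasting 7 days or less: Grade 4 neutropenia with fever or infection, and bleeding with platelets from 10,000 to below 25,000/µL.

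The conclusion assumes that the grade in the two Grade 3 bullets is read literally, that the complication is confined to the Grade 4 interval and meets no 8.2.4 trigger, and that the patient passes the 8.2.1 gate with at most a 1-week delay.

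The dose differences are the steps of Table 0-1, not an estimate of how many patients are affected; the protocol gives no basis for one. The gap is narrow and has no effect on sample size, error rates or the primary analysis. It should still be corrected, because this is a mandatory safety rule used across sites.

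**What to change.** In Section 8.2.3, insert *or greater* directly after *Grade 3* in the neutropenia bullet with fever or infection and in the thrombocytopenia bullet with bleeding. Leave the action unchanged. Keep the two Grade 4 bullets with the more-than-7-day condition for uncomplicated cytopenia, and keep the platelet bullet at 10,000/µL. With this wording every *no trigger* cell in the table above becomes a reduction.

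The cost is two added words in each of two bullets, made by amendment. No extra patients, visits or tests are needed.
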